- Photos (Extra and intra oral).
- Pain questionnaire distributed with explanatory session on it.

➤ **Begin of Retraction:**

- Crimpable hooks added to the arch wire (0.017"x0.025" Stainless steel) distal to the lateral incisor passing near the center of resistance of the anterior segment.
- A ligature wire extending between the second premolar and miniscrews will be used for proper anchorage control.

- Retraction will start on a 0.017"x0.025" Stainless steel wire using elastomeric chain (force applied will be 200 g per side) (24) extending between the crimpable hooks and the molar hooks.
- The force will be measured by a force gauge and reactivated every 4 weeks maintaining constant force of retraction all over the retraction phase.

➤ **Follow up visits**

Patients will be asked to attend for follow up sessions every 4 weeks for:

- Evaluation of miniscrews stability.
- Replacement of the power chain to maintain a force of 200 gm per side for en masse group and 160 gm per side for two step group.
- Impression taking to assesses amount of space closure.
- Recording the pain scoring sheet.

➤ **Criteria for discontinuing or modifying the allocated intervention:**

In cases of prolonged swelling or pain related to the miniscrew, the patient will be given strict oral hygiene measures and may wait for three weeks before the beginning of retraction.

In cases of loose or broken miniscrews, the screw will be removed and replace the miniscrew after total resolution of the inflammation.

In case of non compliant patients.

□ **Post-retraction Questionnaire:**

The patients of both groups will be asked to fill in questionnaires regarding their experience with their allocated technique, during the whole retraction period from day of extraction till the end of retraction.

□ **Retraction records**

Following en-masse and two steps retraction, patients will be referred to the same radiology center to acquire the final cone-beam CT to assess the movement and inclination of anterior teeth.

The final dental model will be used to assess the rate of retraction and molar anchorage loss achieved throughout the study.

□ **Criteria of ending the retraction**

- Class I canine relation
- Normal overjet
- Balanced facial profile
- Closing extraction space

□ **Material Used**

- American Orthodontics Brackets, Roth prescription, 22 slot size.
- American Orthodontics Elastomeric power chains
- American Orthodontics Elastomeric O-ties
- American Orthodontics Ligature wire.

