- Miniscrew, 8 mm length x 1.6mm diameter TAD (Jeil).
- American Orthodontics Arch wires.
- American Orthodontics Molar bands/tubes.

D] Outcomes

[figure not shown]
Primary outcome: is to monitor the Duration of space closure during en-masse and two steps retraction. All outcomes will be assessed as the difference between T0 at the start of retraction and T1 after complete space closure.

Secondary outcomes: is to monitor the changes in the anterior teeth position (final anterior teeth tip, torque and vertical position), anchorage loss, presence of any root resorption and pain associated with the different methods used for retraction.

E] Participant timeline:

1. The principle investigator will screen the potential patients through careful clinical examination of patients at the orthodontic department, Faculty of Oral and Dental Medicine, Future University in Egypt.
2. All recruited patients should fulfil the previously mentioned inclusion and exclusion criteria.
3. Every participant will be asked to sign an informed consent before the beginning of the study.
4. After patient's enrolment, each participant will be asked for pre-intervention records to ensure proper diagnosis.
5. The principle investigator will randomly allocate the patients to one of the intervention groups.

6. Anchorage will be secured by placement of miniscrew, followed by extraction of the first premolar.
7. Active intervention will begin after proper levelling and alignment of the upper arch.
8. The principle investigator will take pre-retraction records for every participant T0.
9. Power chain is used for anterior segment retraction.
10. Each patient will come every 4 weeks for follow up visit, for appliance activation and uptake of impression for interim records + monitoring of recording the VAS sheet.
11. After complete space closure, the principle investigator will take post-retraction records for each participant T1.
12. Every patient will fill up a questionnaire regarding his experience during treatment.
13. The principle investigator will continue the normal treatment and achieve proper finishing for every patient after the end of the study.

F] Sample size calculation:

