Assignment to either intervention will occur before levelling and alignment stage.

D] Blinding:

Blinding of the operators: Blinding will not be possible for the operators during the application interventions and during the follow up visits. The principal operator is responsible for assigning subjects to interventions according to the concealed allocation, appliance activation at follow up visits, dental impressions and acquisition of dental casts.

Blinding of the outcome assessors: It is a single blinded study, therefore, only the outcome assessors will be blind. The patients name will be sealed from pre and

post radiographs and study models. Then two assessors will carry out, blindly and independently, the measurements and analysis of the study.

III) Data collection, management and analysis:

A] Data collection methods:

Primary outcomes:

1. Total Retraction Duration: to assess the timing of antero-posterior movement of anterior teeth and first molars, the principle investigator will take study models for every participant monthly during the follow up visits. Then will digitize the models and identify the landmarks, reference lines and planes on the pre, interim and post-retraction digital dental models for measurements reading. Also, by identifying the landmarks, reference lines and planes using CBCT taken before and after the completion of retraction.

Secondary outcome:

1. Anchorage loss: will be accessed by the principal investigator via CBCT taken before and after the completion of retraction by identifying the landmarks, reference lines and planes, then will interpret the measurements in degrees and millimeters.

2. Pain: Each patient will fill a questionnaire regarding his treatment experience in a VAS scoring from 1-10. The questionnaire will include several questions related to oral hygiene, pain and discomfort experienced throughout the trial.

B] Data management:

A colleague outside the research team will enter the data and organize it in excel sheets in the computer of the orthodontic department.

Data will include all photographs, models, radiographs and filled questionnaire.

C] Statistical Analysis:

- The principle investigator will be responsible for the extraction of the required data from the CBCT taken before and after retraction as well as the study models taken at every follow up visit. The data will be sent to a specialized statistician.

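### The primary end date (T1) has no closure tolerance and no named masked assessor, so someone who knows the arm could set it

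*Combined protocol and SAP*

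**What the plan says.** **End point.** Section I) D] Outcomes makes duration of space closure the primary outcome and adds: "All outcomes will be assessed as the difference between T0 at the start of retraction and T1 after complete space closure". Item 11 of section I) E] Participant timeline reads: "After complete space closure, the principle investigator will take post-retraction records for each participant T1".

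**Measurement.** The outcome measure table gives two sources for duration: digital models taken monthly, measured in mm with 3Shape software, and the computerised visit record. Section I) C], Follow up visits, schedules at each 4-weekly visit: "Impression taking to assesses amount of space closure".

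**Ending retraction.** Section I) C] also lists four criteria for ending retraction: Class I canines, normal overjet, closure of the extraction space, and "Balanced facial profile". None has a numerical cut-off.

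**Roles.** Item 5 of the timeline says: "The principle investigator will randomly allocate the patients to one of the intervention groups". Section II) D] Blinding states that operators cannot be blinded at follow-up visits, and that "The principal operator is responsible for assigning subjects to interventions according to the concealed allocation". For the primary outcome, section III) A] has the principal investigator take the models monthly and continues: "Then will digitize the models and identify the landmarks, reference lines and planes on the pre, interim and post-retraction digital dental models". Section III) C] gives the same role the extraction of data from the models of every visit.

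**Masking.** Section II) D] seals patient names on pre and post radiographs and study models, then says: "Then two assessors will carry out, blindly and independently, the measurements and analysis of the study". It does not mention the date of closure.

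**The concern.** The primary outcome is a length of time, so its validity depends on how the two ends are dated. This point concerns T1 only. The plan names a ruler (mm on digital models) but not the reading on it that means closed, and it does not say whose reading counts.

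When extraction space is nearly shut, one clinician may call it closed today and another at the next visit. If the person making that call knows the arm, the recorded end can differ between arms for reasons unrelated to tooth movement. That is detection bias on the sole primary endpoint of a small trial. Masked measurement of the final model does not remove it if an unmasked person has already chosen which visit was final.

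**Working it through.** **1. Who can set the date, as the roles are written**

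- Knows the arm: the principal investigator (timeline, item 5) and the principal operator (II) D]). Both are given the task of assigning patients, so they appear to be one person. That is an inference; the plan does not say so.
- Takes the T1 records: the principal investigator (timeline, item 11). Taking them presupposes that closure has already been declared.
- Landmarks the pre, interim and post models and extracts the data: the principal investigator (III) A] and III) C]).
- Masked: two assessors (II) D]), with sealed names specified for pre and post records. Interim models, on which the first closed visit would be found, are not named.
- Residual space that counts as closed: not stated in any section.

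Following these roles literally, an arm-aware person can choose the visit that ends the primary duration.

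**2. The plan's own sample size**

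Inputs from section I) F]: SD 0.76, difference 1.0, power 0.8, alpha 0.05 (two-sided assumed).

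n = 2 × (1.960 + 0.842)² × 0.76² / 1.0² = 2 × 7.85 × 0.5776 = 9.07, rounded up to 10 per group. This reproduces the plan. The exact t-test power is 0.795 at 10 per group and 0.935 at 15.

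**3. What one visit is worth**

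Visit interval: 28 / 30.4375 = 0.92 month. Section I) F] gives no unit for the 1.0.

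- If months: one visit is 0.92 of the planned difference.
- If weeks: one visit is 4 times the planned difference.
- If mm or a rate: no comparison can be made.

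**4. Illustration, assuming months**

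Suppose some patients in each arm are dated one visit late. The bias in the difference of means is

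b = 0.92 × (share late in one arm − share late in the other).

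Equal shares give b = 0. For unequal shares with no true difference, the chance of a significant two-sided t-test follows from the noncentral t with noncentrality b / (0.76 × √(2/n)), holding the SD at 0.76:

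| Difference in shares (assumed) | b, months | False-positive rate, n = 10 per arm | n = 15 per arm |
|---|---|---|---|
| 0 | 0 | 5% | 5% |
| 10 points | 0.09 | 5.8% | 6.2% |
| 25 points | 0.23 | 9.8% | 12.6% |
| 50 points | 0.46 | 25% | 36% |

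Nothing in the documents indicates which row, if any, would apply.

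**The case against.** **Closure is already measurable, and complete is a criterion.** The outcome table names tool, unit and software, and the plain meaning of complete closure is no remaining space. This stands in part: a reader might infer that the plan has no way of measuring closure, and that would be wrong. What is missing is narrower, namely the tolerance and the person who sets the date. A zero gap still needs a tolerance once measurement error is admitted; the Assessors Reliability section itself treats disagreement above 1 mm as the trigger for review.

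**Masking is already provided.** The assessors' remit is worded generally and could cover every model. That reading is possible, and for this reason the documents do not show that closure will be judged unmasked. They only leave it open: the sealing sentence names pre and post records, no sentence links the assessors to T1, and landmarking and extraction for the primary outcome go to the principal investigator.

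**The facial-profile criterion could end the duration with space still open.** A reader might infer this from the ending list, but the documents do not say it. The list includes closure and can be read as requiring all four items, and the timeline takes T1 records only after complete closure. The joint reading is also an inference, so the list should be kept out of the definition of T1.

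**The loose rule must cost power.** This is tempting but unsupported. The SD of 0.76 comes from a previous study; if those were recorded durations, it may already contain end-date noise, and adding more would count it twice. No power loss is claimed here.

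**Conclusion.** The point holds in a limited form. The plan says how space closure is measured but not what residual space is complete closure, nor who dates it, and its allocation of roles allows an unmasked person to set the primary end date. The risk is detection bias of unknown size and direction. Bias arises only if dating differs between arms; equal looseness in both arms gives none. The comparison of one visit (0.92 month) with the planned difference of 1.0 depends on that figure being in months, and the error rates shown depend on assumed shares. This is a cheap improvement to the primary endpoint, not evidence that the result will be biased.

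**What to change.** In sections I) D], II) D] and III) A], state that:

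- T1 is the date of the first 4-weekly digital model on which the two existing masked assessors, reading coded scans (interim models included), measure residual upper extraction space at or below one tolerance in mm on both sides.
- The tolerance is fixed before any outcome model is read, is no smaller than the repeat-measurement error, and applies identically in both arms. The planned repeat exercise mentions a single model and gives no date, so run it beforehand on several routine clinic models.
- The principal investigator takes impressions and supplies coded scans but does not set the date.
- Canine relation, overjet and facial profile remain clinical goals and do not enter the primary duration.
- Any patient whose retraction ends with space above the tolerance is reported by arm and not counted as closed.

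**Cost.** No new staff, visits or impressions. If each patient's last three models are read, going further back only when all three are closed, that is 30 × 3 = 90 models, and 90 × 2 = 180 readings. A reliability exercise on 10 models (assumed) adds 10 × 2 assessors × 2 readings = 40.

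**Downsides.** T1 may differ by a visit from the clinical end of retraction. A tolerance slightly relaxes complete closure. The position of the gap on interim models may partly reveal the arm, which is why a fixed cut-off matters as well as masking. A patient not counted as closed has no observed T1, so the plan should also say how that patient enters the comparison.

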Our sample size calculation is based on a previous study comparing the effect of En masse versus two-steps using friction and frictionless mechanics²⁴. Using PS software output, we are planning a study of a continuous response variable from independent Group I and Group II subjects with 1 Group I(s) per Group II subject. In a previous study the response within each subject group was normally distributed with standard deviation 0.76. If the true difference in the Group II and Group I means is 1.0, we will need to study 10 Group II subjects and 10 Group I subjects to be able to reject the null hypothesis that the population means of the Group II and Group I are equal with probability (power) 0.8. The Type I error probability associated with this test of this null hypothesis is 0.05. Considering drop out a sample size 15 per group is appropriate.

G] Recruitment strategy:

The principal investigator will recruit the patients from the clinic of Orthodontic department, Faculty of Oral and Dental Medicine- Future University in Egypt. Screening of patients will continue until the total number of participants for the study is collected.

II) Assignment of interventions:

A] Sequence generation:

The supervisor of the study will apply Computer generated random numbers to randomly assign patients to group A (En-masse) or B (two steps) using Microsoft Office Excel 2007 sheet. The patient numbers will be written in the first column and the supervisor will select function RAND to generate the randomization

number in the second column. These numbers will be sorted according to the randomization number so the first column numbers will be randomly distributed.

B] Allocation concealment mechanism:

The Co-supervisor of the study ([name]) will write the randomization numbers of the patients on opaque white papers folded three times to form sealed envelopes and store it inside a box. The codes for randomization will be securely held at the secretary's office.

C] Implementation:

At the time of intervention, the main operator will send the patient to the secretary's office. Then, the assigned employee will open the box and ask the patient to select one envelope. The main operator will contact the supervisor to know the order and then the main operator will allocate each patient to assign each participant for the corresponding intervention either (En-masse or two steps group) according to the list of codes of randomization.

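### Patients pick a folded paper from a box and the unblinded operator makes the final allocation, with no numbered order, draw log or reconciliation described

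*Combined protocol and SAP*

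**What the plan says.** All references are to the combined protocol and SAP.

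- **II) A] Sequence generation.** The supervisor lists patient numbers in Excel, attaches RAND values and sorts on them. How the sorted list is divided between the two arms is not stated.
- **II) B] Allocation concealment mechanism.** The co-supervisor "will write the randomization numbers of the patients on opaque white papers folded three times to form sealed envelopes" and stores them in a box. "The codes for randomization will be securely held at the secretary's office".
- **II) C] Implementation.** The main operator sends the patient to that office. "Then, the assigned employee will open the box and ask the patient to select one envelope". After that, "The main operator will contact the supervisor to know the order and then the main operator will allocate each patient", following the list of codes. The section ends by placing assignment ahead of levelling and alignment.
- **I) E] Participant timeline, step 5.** "The principle investigator will randomly allocate the patients to one of the intervention groups".
- **I) G] Recruitment strategy.** "The principal investigator will recruit the patients from the clinic of Orthodontic department".
- **II) D] Blinding.** Operators cannot be blinded. The principal operator is responsible for assigning subjects, in line with the concealed allocation.
- **IV) D] Auditing.** The supervisor periodically follows up trial progress, including allocation to groups. No record to check against is named.

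**The concern.** Concealment by envelopes normally rests on two things: the next assignment is fixed before the patient is known, and someone outside the treating team records it. Here the sorted list could have fixed the order, but the patient's free pick sets it aside. The list alone then cannot show which arm a given patient should have received. The last step, turning a number into an arm, lies with an operator who treats the patient and cannot be blinded.

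If a draw were repeated, an assignment changed or a patient dropped once the arm was known, nothing described in the plan would reveal it. The primary outcome is duration of space closure, and with about 30 patients a few such cases could move the comparison. The statistical section does not commit to analysing every patient in the allocated arm, so that safeguard is missing as well. None of this can be repaired after enrolment.

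**Working it through.** **1. The procedure, step by step**

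| Step | Who | What is described | What is not described |
|---|---|---|---|
| Generate list | Supervisor | Excel RAND and sort | How the list is split between arms; freezing the list |
| Prepare papers | Co-supervisor | Opaque, folded, called sealed; carry numbers | Sequential order of use |
| Hold codes | Secretary's office | Secure custody | Why the supervisor is then asked for the order |
| Draw | Assigned employee and patient | Patient selects one paper | Registration before the draw; log of number and date |
| Convert number to arm | Main operator, after contacting the supervisor | Allocation by the list of codes | Arm issued and recorded by someone other than the operator |
| Check | Supervisor (IV) D]) | Periodic follow-up | Reconciliation of draws with the list |

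Two internal differences follow.

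- **Custody.** B] puts the codes at the secretary's office, but in C] the operator goes to the supervisor for the order.
- **Timing.** C] opens by placing the draw at the time of intervention and closes by placing assignment before levelling and alignment. Timeline step 5 fits the latter. Step 7 says active intervention starts after levelling, so the opening of C] does not fit unless intervention there means the start of treatment as a whole.

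**2. The plan's own figure**

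Inputs from I) F]: difference 1.0, SD 0.76 (units not stated), power 0.80, alpha 0.05 (two-sided assumed).

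n per group = 2 × 0.76² × (1.960 + 0.842)² / 1.0² = 9.07, rounded up to 10. The noncentral t gives 10.12 and a power of 0.795 at 10 per group. The stated 10 reproduces to within rounding, and the allocation procedure does not affect it.

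**3. Illustration of what undetected exchanges could do**

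Inputs: 15 per arm (I) F]) and the two-sample t-test that the sample size assumes. Three things are assumed and not in the documents:

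- k exchanges occur, all in the same direction.
- In each, a patient judged 1 SD slower than average goes to two-step instead of en-masse, in exchange for an average patient.
- The operator's prognosis correlates r with actual duration.

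Each exchange lowers one arm's mean by r/15 SD and raises the other's by r/15 SD. The shift is therefore 2kr/15 SD. The noncentrality is the shift × √(15/2) = shift × 2.739, with 28 degrees of freedom and critical value 2.048. The within-arm SD is taken as unchanged.

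False-positive rate, with the shift in SD in brackets:

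| Exchanges k | r = 0.3 | r = 0.5 | r = 1.0 |
|---|---|---|---|
| 1 | 5.1% (0.04) | 5.4% (0.07) | 6.4% (0.13) |
| 2 | 5.5% (0.08) | 6.4% (0.13) | 10.9% (0.27) |
| 3 | 6.2% (0.12) | 8.3% (0.20) | 18.5% (0.40) |

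On the plan's SD, two exchanges shift the difference by 0.267 × 0.76 = 0.20 at r = 1.0, one fifth of the planned 1.0. At r = 0.3 the shift is 0.08 × 0.76 = 0.06.

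**The case against.** The plan has more protection than a quick reading suggests, and most of the defence stands.

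- **Third parties are involved.** The supervisor, the co-supervisor, the secretary's office and an assigned employee all have a part. A reader might infer that assignment is wholly in the operator's hands. The text does not support that: the operator must contact the supervisor and follow the list.
- **The papers are described as sealed.** The text has "opaque white papers folded three times to form sealed envelopes". One may doubt that folding seals anything, but the plan cannot be reported as using unsealed papers. They also carry numbers, so opening one does not reveal an arm without the codes.
- **The draw comes before the arm is known, in front of an employee.** Picking blindly from a box is a chance mechanism. A reader might infer non-random assignment; the documents do not show it.
- **A check is possible in principle.** Numbered papers map to a list of codes, and the supervisor follows up allocation. It would be wrong to say that assignment cannot be audited.
- **The operator is not stated to be the recruiter.** The recruiter is the principal investigator, and the allocator is the main or principal operator. The timeline also has the investigator allocate, so they are probably the same person, but no passage says so.
- **The larger false-positive rates need perfect prognosis.** The documents give no baseline predictor of duration, and at a correlation of 0.3 the inflation is small.

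What the defence does not supply is a fixed order of use, a registration step, a written record of each draw, or an arm issued by someone other than treating staff. A witness without a log leaves nothing to reconcile later.

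**Conclusion.** The point holds as a weakness of concealment and auditability. The patient's pick removes the link between enrolment order and list, the unblinded operator makes the final allocation, and no numbering, prior registration, log or reconciliation is described. The sections also need reconciling on custody of the codes and on timing. The documents support neither of two stronger conclusions: that assignment is non-random, or that tampering is to be expected.

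The size is conditional. Under the assumptions shown, two exchanges take the false-positive rate from 5% to between 5.5% and 10.9%, and three to between 6.2% and 18.5%. The lower ends may well be the more realistic, since nothing in the plan suggests that duration can be predicted well. The case for change rests less on these figures than on the low cost of closing a gap that cannot be closed later. It should be corrected before enrolment.

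**What to change.** Replace II) B] and C] with the following:

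1. The supervisor freezes the computer list, with an arm against each position, before the first patient.
2. The co-supervisor prepares consecutively numbered, opaque, sealed envelopes, each containing the arm.
3. Once eligibility and consent are logged, the secretary's office writes patient ID and date on the next envelope in order, opens it, logs the arm and informs the operator.
4. The supervisor reconciles the log with the list as part of IV) D].

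Delete the patient's pick and the operator's call for the order. Align timeline step 5, II) C] and the assigning sentence in II) D] on who assigns, and settle one statement of when. Add to the statistical section that patients are analysed in the logged arm.

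The cost is protocol wording and one log sheet. The staff are already named, and the sample size is unchanged. One thing is given up: the plan's present separation of number from arm, since the new envelopes contain the arm. Sealing, numbering and custody by the office offset that loss.

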6. Minimal crowding 2-3 mm.

Exclusion Criteria: for the involved subjects included:

1. Patients suffering from any systemic diseases interfering with tooth movement.
2. Patients with extracted or missing permanent teeth. (Except for third molars).
3. Patients with badly decayed teeth.
4. Patients with any parafunctional habits (i.e. Bruxism, tongue thrusting, mouth breathing, etc...).
5. Patients with previous orthodontic treatment.

C] Interventions:

➤ Medical History Questionnaire:

For every patient, to exclude the presence of any systemic condition interfering with orthodontic treatment.

➤ Clinical Examination:

Oral structures will be examined to identify caries, fracture or missing teeth. Gingival tissues will be carefully examined for any gingivitis, periodontitis, recession, or lesions.

➤ Diagnosis

Check the potential patient to fulfill the previously mentioned inclusion criteria. Every participant will be asked to sign an informed consent about the study. Full set of records (study models, panorama radiograph and lateral cephalometric radiographs, photos) will be taken for every patient as part of the routine procedure for treatment of patients in the clinic of the Orthodontic Department, Future University in Egypt.

➤ Clinical Procedure:

After taking pre-treatment records, every patient will receive:

- Miniscrews will then be placed in the upper arch between the second premolar and first molar.
- The patient will be referred for extraction of first premolars.

- Anchorage will be secured, followed by Leveling and alignment for the bonded and banded teeth through following the wire sequence: 0.014 NiTi, 0.016×0.022 NiTi and 0.017×0.025 StSt.
- Bonding of all teeth except for first premolars and banding/bonding the first and second molars will be done using Roth prescription brackets (0.022 x 0.028 slot)*.
- After leveling and aligning is completed (right before retraction), the patient will be referred for the uptake of pre-intervention records for en masse group (Impression for models, photos extra oral and intra oral and pain questionnaire).
- For two step group canine retraction will take place on a 0.017×0.025 StSt arch wire, once canine retraction stage is completed, the patient will be referred for the uptake of pre-intervention records.

➤ **Acquisition of pre-intervention records:**

- Alginate impressions will be taken before retraction (without the arch wire in place) followed by digital scanning of produced models.

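### Randomisation precedes a levelling phase common to both arms, so the arm is known when readiness for retraction is judged, and patients lost in that phase have no primary outcome

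*Combined protocol and SAP*

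**What the plan says.** **When the arm is assigned.** II) C] Implementation ends with "Assignment to either intervention will occur before levelling and alignment stage". Step 5 of the Participant timeline agrees: "The principle investigator will randomly allocate the patients to one of the intervention groups". Step 6 is miniscrew placement and extraction, and step 7 refers to levelling. The same Implementation section opens more loosely: "At the time of intervention, the main operator will send the patient to the secretary's office".

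**When the arms begin to differ.** Timeline step 7 says "Active intervention will begin after proper levelling and alignment of the upper arch". I) C] Interventions, under Clinical Procedure, lists miniscrews, extraction, bonding and one wire sequence as given to every patient: "Anchorage will be secured, followed by Leveling and alignment for the bonded and banded teeth through following the wire sequence". The arms separate only at retraction, which in the two-step arm begins with the canines.

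**What starts the primary outcome.** I) D] Outcomes: "All outcomes will be assessed as the difference between T0 at the start of retraction and T1 after complete space closure". Timeline step 8: "The principle investigator will take pre-retraction records for every participant T0". Clinical Procedure gives completed levelling as the trigger in the en-masse arm, without a measurable criterion and without naming who declares it.

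**Who knows the arm.** II) D] Blinding: "Blinding will not be possible for the operators during the application interventions and during the follow up visits". Only the outcome assessors are blind, and their blinding concerns measurements on radiographs and models.

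**Losses.** I) F] Sample size calculation raises 10 per group to 15 for dropout. III) C] Statistical Analysis defines no analysis population and no handling of patients who never reach T0.

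**The concern.** Ideally, randomisation comes as close as practicable to the point where the treatments diverge. Here a whole treatment phase, identical by design, lies between the draw and the first difference between arms. No purpose is stated for knowing the arm during that phase.

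Two things are at stake:

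- **Comparability at T0.** Judging a patient ready for retraction leaves room for discretion, and it is exercised with the arm known. If levelling is taken further in one arm, or residual extraction space differs between arms when retraction starts, the arms begin the timed period from different positions.
- **Integrity of the randomised groups.** A patient who leaves during levelling has been randomised but can contribute no duration. Without a rule, such patients simply disappear from the primary comparison, and the groups analysed are not the groups randomised.

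**Working it through.** **1. Order of events.** Combining the Participant timeline with Clinical Procedure:

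| Event | Timeline step | Differs by arm? |
|---|---|---|
| Allocation | 5 | – |
| Miniscrews, extraction | 6 | No |
| Levelling and alignment | before the start in 7 | No |
| T0 records | 8 | Not in the timeline; see step 5 below |
| Retraction | 9 | Yes |

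Everything between allocation and the T0 records is common treatment given with the arm known.

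**2. Who judges readiness.** The documents name nobody. The principal investigator takes the T0 records, the principal operator runs activation visits and takes impressions, and the assessors are given measurements only. That the operator makes the judgement is therefore an inference, though no other role is given it.

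**3. What knowledge of the arm can change.** The outcome is duration = T1 − T0, with T0 the actual start of retraction. If the start is put back by a time d and nothing else changes, duration = (T1 + d) − (T0 + d) = T1 − T0. A later start alone leaves duration unchanged. An effect needs a second step: a different degree of levelling, or different residual space, at T0. The documents contain no figures from which to size this.

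**4. What losses before T0 cost in power.** Inputs from Sample size calculation: SD 0.76, difference 1.0 (units not stated), alpha 0.05 (two-sided assumed), power 0.80.

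- The plan's figure: n = 2 × [0.76 × (1.960 + 0.842) / 1.0]² = 9.07, so 10 per group. It reproduces.
- Implied loss allowance: (15 − 10) / 15 = 33%.
- Power by the noncentral t distribution, with df = n₁ + n₂ − 2 and noncentrality 1.0 / [0.76 × √(1/n₁ + 1/n₂)]:

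| Patients with a duration, per arm | Power |
|---|---|
| 15 and 15 | 93.5% |
| 12 and 12 (20% lost) | 86.9% |
| 10 and 10 (33% lost) | 79.5% |
| 9 and 9 (40% lost) | 74.6% |
| 15 and 10 | 87.0% |
| 12 and 10 | 83.2% |

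Up to one-third total loss, power stays at about the planned level, and a moderate imbalance costs little. The issue is which patients remain, not how many.

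**5. A neighbouring conflict.** Clinical Procedure takes the two-step arm's pre-intervention records after canine retraction, whereas Outcomes and timeline step 8 place T0 at the start of retraction. This is a separate matter, and moving the draw does not resolve it.

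**The case against.** **A later start shifts both ends of the interval.** This stands. A reader might infer that declaring T0 one 4-week visit early or late moves the duration by 28/30.44 = 0.92 month, so that doing so in a fifth of one arm shifts the mean by 0.2 × 0.92 = 0.18 month. The documents do not support that. It holds T1 fixed while T0 moves, and it also assumes both a month unit and a misdating fraction that the plan does not give.

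**Discretion is limited.** The wire sequence ends on the same wire on which retraction begins. That narrows the judgement but does not settle it, since no criterion for completion is given.

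**The plan does not really contradict itself.** This largely stands. The opening and closing sentences of Implementation can be read together, the second specifying the first, and timeline step 5 agrees with the second. A reader might infer two incompatible randomisation times; the wording supports no more than a point to tidy.

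**Losses during identical treatment are not in themselves biasing.** True, and nothing in the documents predicts unequal loss. But patients are not blinded, so unequal loss is possible, and the plan has no rule for those without a T0.

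**The gain is partial.** Also true. The operator remains unblinded up to T1, whose criteria include judgements such as facial profile. Later randomisation protects the start of the interval, not its end.

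**Conclusion.** The point holds as an avoidable weakness of design. It is well supported that allocation comes before a common treatment phase, that the operator is unblinded through it, and that a patient lost in it has no observable primary outcome and no rule for analysis. That the operator judges readiness for retraction is an inference.

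No size can be put on any effect on duration. It would act only through the state of the dentition at T0, and the documents give nothing from which to estimate that. The power cost is small: 79.5% remains at one-third loss, assuming a two-sided test and the plan's own SD and difference.

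This does not make the primary comparison invalid. It is worth changing because the change is specific and cheap, and deals with both consequences together. A defined T0 criterion confirmed by someone blind to the arm would protect the start of the interval, but would leave randomised patients without an outcome.

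**What to change.** Draw the envelope once three things are done in every patient: levelling is recorded as complete, with the role that records it named; the end-of-levelling model is taken; and the pain sheet is completed. The draw then comes immediately before any retraction starts, canine retraction included.

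Wording changes:

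- Replace the closing sentence of II) C] Implementation to say this, so that it agrees with the section's opening.
- Move timeline step 5 to after the end-of-levelling records and before step 9. Placing it directly after step 7 would put the draw ahead of the step 8 records.
- State the primary analysis population as all randomised patients, with a rule for those who start retraction but do not reach T1.
- Reconcile separately when the two-step arm's pre-intervention records are taken (Clinical Procedure against Outcomes and timeline step 8).

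Cost: no extra visit and no change to the sample-size formula. Patients lost during levelling are never randomised, so there are two options:

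- **Keep enrolment at 30.** Some envelopes go unused. With 3 undrawn, for example, the split could be as uneven as 15 and 12. The number completing is not reduced by drawing later.
- **Randomise 30.** Enrolment rises to 30/(1 − f), where f is the fraction lost in levelling. As an assumed range, f = 10% gives 33.3, so 34 patients, and f = 20% gives 37.5, so 38.
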